7 PATIENT REGISTRATION

Patient enrollment will take place over 24 months at a single institution-Indiana University Simon Cancer Center (IUSCC)/Indiana University Hospital (IUH).

All patients will be registered with the Indiana University (IU) Department of Urology. Regulatory files will be maintained by the Department of Urology. Applicable regulatory documents must be completed and on file prior to registration of any patients. Potential patients will be identified in the Urology clinic or by physician referrals. Patients who appear to be eligible for this trial will undergo the Informed Consent Process and be screened for eligibility utilizing the Eligibility Criteria. Individual patient registration will be done in the OnCore[®] database. The original signed Institutional Review Board (IRB) approved Informed Consent Document and completed eligibility checklist will be stored in the following location:

Indiana University Medical Center
Indiana Cancer Pavilion
Urology Clinic, 3rd floor
[name]
[name]

8 STUDY PROCEDURES

8.1 Summary

Administration of the study drug will begin prior to skin incision in the preoperative area where safety monitoring will occur. The tumor resection occurs approximately 2 hours after being brought back to the operating room and so there is no wait time between infusion and being taken back to operating room. Intraoperative fluorescent imaging will be utilized in parallel with the standard operating procedure to capture images during surgery. Images also will be taken of the excised specimen on the back table. The excised specimen will be sent to the pathology department for fluorescent imaging and immunohistochemistry for FR. Subjects will have a 2-5 day hospital stay (normal nephrectomy recovery period) where safety measurements will be taken. Final safety measurements will be taken at the 10-day and 1-month follow-up visits.

8.2 Study calendar

Study Procedures ¹²	Screening	Pre-surgery	Surgery	Post-surgery	Hospital Admission	Hospital Discharge	Follow-up Phone Call	Follow-up Appt
	Up to 90 days prior to surgery	Day 0			Days 1-5	Days 2-6	Day 10 (± 3 days)	1 Month (±14 days)
Informed consent	X							
Inclusion/exclusion criteria	X							
Demographics	X							
Medical history ¹	X	X ²						
Physical exam	X							X
Height/weight	X							X ³
Vital signs ⁴	X	X ⁵	X ⁶	X ⁶	X ⁶	X ⁶		X
Urine/serum pregnancy test	X ⁷	X ⁸						
Complete metabolic panel (CMP)								X
Basic metabolic panel (BMP) ⁹	X				X ¹⁰			
CBC w/ diff	X				X ¹⁰			X
Study drug administration ¹¹		X						
Surgery with associated procedures including intra-operative imaging			X					
Tumor ex-vivo sample collection			X					
Pathologic assessment				X				
PI Likert questionnaire				X				
AE assessments		X	X	X	X	X	X	X
ADE assessments			X	X	X	X	X	X
Concomitant medications	X	X ¹	X	X	X	X	X	X

Footnotes:

¹Includes past medical history, past surgical history, allergies and any ongoing medical conditions

²Since screening visit and up to 30 days before surgery

³Weight only

⁴Temperature, blood pressure, respiratory rate and pulse rate

⁵Taken at baseline (up to 30 minutes prior to OTL38 infusion), approximately every 15 minutes during infusion (only blood pressure and pulse rate), and then approximately every hour after infusion until surgery is initiated

⁶Record per institutional practice

⁷Serum pregnancy test for all females of childbearing potential

⁸Urine pregnancy test for all females of childbearing potential

⁹Basic metabolic panel includes Na, K, Cl, Mg, Ca, BUN, creatinine

¹⁰Obtain on day 1 after surgery

¹¹Single dose of anti-histamine (diphenhydramine 25 mg IV) will be administered prior to the study drug; study medication will be administered less than 2 hours prior to the skin incision

¹²Patients from both arms will follow this schedule

8.3 Assessments by visit

8.3.1 Screening (Day -90 to Day -1):

- Informed consent: investigators or their designees will discuss with subjects the nature of the study, its requirements, risks, and restrictions to obtain informed consent for participation in the study. Subjects should have sufficient time to review the study information and consent form and to ask any questions necessary to make an informed decision regarding their participation in the study. Written informed consent is to be obtained before any other study-specific procedure.
- Eligibility criteria: make sure patient meets study eligibility criteria.
- Demographics
- Medical history: includes past medical history, past surgical history, allergies and any ongoing medical conditions
- Medication history: all medications noted in patients record at time of screening
- Physical examination: including height, weight, vital signs (blood pressures, heart rate, respiratory rate, and temperature). The extent of the physical examination is determined by the investigator (or designee) and is based on clinical relevance to the subject's medical history and scheduled surgical procedure as per standard medical/surgical care.
- Blood samples: complete blood count with differential (CBC w/ diff) and basic metabolic panel (Na, K, Cl, Mg, Ca, BUN, creatinine), and serum pregnancy for women of childbearing age

8.3.2 Surgery (Day 0):

8.3.2.1 Pre-surgery:

- Eligibility criteria: ensure subject continues to meet study eligibility
- Medical history: capture additional medical history since screening
- Concomitant medications: record medications taken since screening through day of surgery. All preoperative medications (this does not include normal saline or other routine maintenance intravenous fluids) will also be recorded.
- Urine pregnancy test: for women of childbearing age
- Vital signs (blood pressures, heart rate, respiratory rate, and temperature): will be taken at baseline (up to 30 minutes prior to infusion), approximately every 15 minutes during infusion (blood pressure and pulse rate), and then approximately every hour after infusion until surgery is initiated. During and post-surgery these will be recorded per institutional practice.
- Study drug administration:
 - A single dose of anti-histamine (diphenhydramine 25 mg IV) will be administered prior to the study drug.
 - Begin administration of study medication less than 2 hours prior to the skin incision on day of surgery in the preoperative area.
 - Record time of study medication administration
 - Record time of scheduled surgery (listed operating room time)
- AE assessment: including hypersensitivity reactions, which could include skin reactions, difficulty breathing, eye or nasal reactions, or gastrointestinal complaints, redness, tenderness, pain, or rash at the injection site or any clinically relevant abnormality (with exception of surgical scars) noted after the start of the study medication that was not present at screening.

8.3.2.2 Surgery:

The da Vinci[®] Fluorescence Imaging Vision System, SPY Elite Imaging System or Visionsense VSiii 3DHD system will be used to identify tumor lesions under normal/visible light and fluorescent light prior to surgical excision of lesions, and again after surgical excision of lesions to identify persistent lesions. The da Vinci system or Visionsense VSiii system will be used for all partial nephrectomies (robotic) and for robotic radical nephrectomies. The SPY Elite will be used for open radical nephrectomies. See **Appendix D** and **Appendix E** for more detailed information about the da Vinci and SPY camera/imaging systems. Information about the Visionsense VSiii system can be found at <http://www.visionsense.com/vsiii-system/>.

The Investigator will record the start and stop time for each exposure to fluorescence (pre-resection, post-initial resection, other [give reason]) in the eCRF. The total time of fluorescence will be calculated automatically.

Status	Time On Fluorescent Light	Time Off Fluorescent Light
Before surgical excision		
After initial surgical excision		
Other (explain reason)		

The number and location of suspect tumor lesions detected under **normal light and/or by palpation** will be recorded on the schematic (**Appendix B**) using an “O”. The number and location of suspect tumor lesions detected using **fluorescent light** will be recorded on the schematic using an “x” (for those lesions that were also identified under normal light and/or by palpation, the “x” will be superimposed on the “O” as “⊗”; and for those identified only under fluorescence, they will be recorded only by the “x”).

Light source	Notation
Visible light	O
Fluorescent	X
Both	⊗

For Partial Nephrectomies

Surrounding perinephric fat will be removed as indicated for the renal mass. Then the renal mass will be visualized and photographed (video and still images) using visible light and fluorescent light. As described above, start and stop times of exposure to fluorescent light will be noted, and the number and location of fluorescent lesions related to the mass and surrounding renal parenchyma detected will be recorded on the schematic. Findings under visible light will also be recorded.

After the renal mass is removed, it will be processed by the operating surgeon and the frozen section pathology staff. The tumor margin will be inked and the tumor sectioned in 5mm thick cross-sectional slices. The tumor will then be returned to the operating room to be viewed and photographed with visible and fluorescent light. It will then be sent for pathologic processing as discussed in **Appendix B**.

For Radical Nephrectomies

The regional lymphadenectomy will be performed as per the standard of care for the patient’s renal mass. The renal mass will be visualized and photographed (video and still images) using visible and fluorescent light *through the surrounding perinephric fat*. The start and stop times of exposure to fluorescent light will be noted, and the number and location of fluorescent lesion/s related to the mass and surrounding renal parenchyma detected under fluorescent and visible light sources will be recorded on the schematic.

All identified nodal tissue from each marking (“O”, “X”, and “⊗”) will be excised, as determined by the Investigator, *under normal light*. Following the initial excision under normal light, the field will be illuminated with *fluorescent light* again to detect any remaining fluorescence-positive lesions. Any such lesions will be noted with a “P” on a schematic sheet (**Appendix C**) and excised as determined by the Investigator. A unique identifier will be assigned to each excised lesion, and the location for each lesion will be recorded on the schematic and in the eCRF. The reason for not excising any remaining lesion(s) will be noted. If no additional lesions are observed, this will be noted on the schematic and in the eCRF.

The nodal tissue will be processed by the operating surgeon and the frozen section pathology staff. The lymph nodal tissue will be marked with suture or clips to help with anatomic orientation of the specimen, and then sent for pathologic processing as discussed in the study pathology manual.

To further assess agreement of gross fluorescence with pathology, at least one representative lymph node biopsy done. Once the specimen is removed, it will be processed by the surgical team on the back table and sent to pathology for microscopic examination and immunohistochemistry assessment to determine if it contains FR α + cancer cells. The pathologist will be blinded to the fluorescence results of the tumor.

For All Surgeries

- Vital signs: recorded per institutional practice
- AE assessment: including hypersensitivity reactions, which could include skin reactions, difficulty breathing, eye or nasal reactions, or gastrointestinal complaints, redness, tenderness, pain, or rash at the injection site or any clinically relevant abnormality (with exception of surgical scars) that was not present at screening.
- Adverse device effects (ADE) assessment: the surgeon will examine the subject to confirm that there are no visible changes to skin (erythema or pigment darkening), tissue or organs related to fluorescence. Changes could be present but are likely due to the temperature of the cauterization as lesions are excised.
- Concomitant medications: record all intraoperative medications (this does not include normal saline or other routine maintenance intravenous fluids)

8.3.2.3 Post-surgery:

- Post-surgery questionnaire: the surgeon will complete a questionnaire describing the usefulness of the fluorescence imaging for tumor removal and to achieve a negative margin (**Appendix A**).
- Blinded surgeon assessment: A co-investigator, blinded surgeon who was not involved with the case will view the photographs and complete a questionnaire to assess inter-observer agreement (**Appendix A**).
- Type of RCC excision (radical, partial), need for blood transfusion and estimated blood loss
- Vital signs: recorded per institutional practice

- AE assessment: including hypersensitivity reactions, which could include skin reactions, difficulty breathing, eye or nasal reactions, or gastrointestinal complaints, redness, tenderness, pain, or rash at the injection site or any clinically relevant abnormality (with exception of surgical scars) that was not present at screening.
- ADE assessment: the surgeon will examine the subject to confirm that there are no visible changes to skin (erythema or pigment darkening), tissue or organs related to fluorescence.
- Concomitant medications: record all postoperative medications (this does not include normal saline or other routine maintenance intravenous fluids)

8.3.3 In-hospital admission (Days 1-5):

- Blood samples: complete blood count w/ differential (CBC w/ diff) and basic metabolic panel (BMP) *on day 1 after surgery*
- Vital signs: recorded per institutional practice
- AE assessment: including hypersensitivity reactions, which could include skin reactions, difficulty breathing, eye or nasal reactions, or gastrointestinal complaints, redness, tenderness, pain, or rash at the injection site or any clinically relevant abnormality (with exception of surgical scars) that was not present at screening.
- ADE assessment: the surgeon will examine the subject to confirm that there are no visible changes to skin (erythema or pigment darkening), tissue or organs related to fluorescence.
- Concomitant medications: record all postoperative medications (this does not include normal saline or other routine maintenance intravenous fluids)

8.3.4 Hospital discharge (Day 2-6):

- Vital signs: recorded per institutional practice
- Review records relating to discharge: date and time that discharge order was written (must occur the same day)
- AE assessment: including hypersensitivity reactions, which could include skin reactions, difficulty breathing, eye or nasal reactions, or gastrointestinal complaints, redness, tenderness, pain, or rash at the injection site or any clinically relevant abnormality (with exception of surgical scars) that was not present at screening.
- ADE assessment: the surgeon will examine the subject to confirm that there are no visible changes to skin (erythema or pigment darkening), tissue or organs related to fluorescence.
- Concomitant medications: record all postoperative medications (this does not include normal saline or other routine maintenance intravenous fluids)

8.3.5 Follow-up phone call (Day 10 [±3 days]):

- AE assessment: including hypersensitivity reactions, which could include skin reactions, difficulty breathing, eye or nasal reactions, or gastrointestinal complaints, redness, tenderness, pain, or rash at the injection site or any clinically relevant abnormality (with exception of surgical scars) that was not present at screening.

- ADE assessment: the surgeon will examine the subject to confirm that there are no visible changes to skin (erythema or pigment darkening), tissue or organs related to fluorescence.
- Concomitant medications: record any new medications taken since discharge
- A letter will be sent to any subject not contacted after 3 attempts by telephone

8.3.6 Follow-up appointment (1 Month [± 14 days]):

- Physical examination: including weight and vital signs (blood pressures, heart rate, respiratory rate, and temperature). The extent of the physical examination is determined by the investigator (or designee) and is based on clinical relevance to the subject's medical history and scheduled surgical procedure as per standard medical/surgical care.
- Blood samples: complete blood count with differential (CBC w/ diff) and complete metabolic panel (CMP)
- AE assessment: including hypersensitivity reactions, which could include skin reactions, difficulty breathing, eye or nasal reactions, or gastrointestinal complaints, redness, tenderness, pain, or rash at the injection site or any clinically relevant abnormality (with exception of surgical scars) that was not present at screening.
- ADE assessment: the surgeon will examine the subject to confirm that there are no visible changes to skin (erythema or pigment darkening), tissue or organs related to fluorescence.
- Concomitant medications: record any new medications since discharge or follow-up phone call

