12.8 Analysis of secondary objectives

Specificity: The analysis for specificity is described above.

Detection of RCC in primary tumor (radical nephrectomy arm only): This analyses will be the same as for the primary objective in the partial nephrectomy arm. Pattern of nodal spread will be described qualitatively.

Agreement between pathological agreement between fluorescence and FR α by IHC: This endpoint will also be assessed by Kappa statistics (for presence/absence) or Intra Class Correlation (for numerical measures). Agreement between nodal and primary tumor fluorescence in the radical nephrectomy arm will be assessed similarly.

Agreement between visual and fluorescent images: Kappa statistics will be used to assess agreement between visual and fluorescent images. In addition, the number of lesions detected by

usual visible/tactile conditions and/or palpation vs fluorescent imaging will be analyzed using a paired t-test.

Inter-observer agreement: Kappa statistics will be used to assess inter-observer agreement between of captured fluorescent images.

Usefulness: Responses to the Likert scale questionnaire completed by the surgeons will be listed and summarized

Safety: Vital signs will be summarized using descriptive statistics. Clinical chemistry, hematology, and urinalysis laboratory values will be listed in tabular format and those with above or below normal range will be identified within the table. AEs and TEAEs will be summarized by body system and presented by severity and causal relationship to study drug. ADEs will be summarized by body system and presented by severity and causal relationship to study device. Patients experiencing serious AEs or serious ADEs will be listed and summarized in tabular format.

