19.4.7 Operation

The da Vinci® Fluorescence Imaging Vision System is used to image OTL38 as follows:

OTL38 is administered 2 to 3 hours prior to scheduled surgery. The agent is rapidly distributed after IV administration and also rapidly eliminated from the circulation. Tissues containing high concentrations of folate receptors sequester the agent.

When illuminated by the NIR excitation light produced by the da Vinci® Fluorescence Imaging Vision System, the tissues containing OTL38 continue to fluoresce while the surrounding tissues become dark. The agent was shown to preferentially label folate-receptor-positive tumors in animal models. Tumors that contain folate receptors will bind OTL38, and the da Vinci® Fluorescence Imaging Vision System will cause the tumors to appear green in the augmented image displayed in the Surgeon Console and on the video monitor. In animal models, tumor-specific fluorescence was shown to last at least 8 hours after administration allowing for post-surgical tumor imaging. Although normal kidney proximal tubule cells contain folate receptors

and uptake of OTL38 in the kidneys is possible, the fluorescence signal in the kidneys is expected to be significantly lower than the tumor tissues ([Ross 1994](#)).

Investigators will employ the device in their procedures as outlined. Once the patient has undergone surgical preparation for a partial nephrectomy and the laparoscope has been inserted into the abdomen, images of the surgical area will be captured using both a fluorescence and white light examination prior to tumor excision. The images will be evaluated to determine the extent of tumor involvement and confirm these assessments with normal visual examinations. Surgery will be performed as per usual protocol/procedure, after which a follow-up image of the surgical field will be captured using fluorescence imaging. The remaining fluorescent tissues will be evaluated for possible tumor involvement and the surgical procedure will be finished as indicated.

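### White-light and palpation findings are not required to be recorded before fluorescence is viewed, so the visual-versus-fluorescence comparison can be biased toward agreement

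*Combined protocol and SAP*

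**What the plan says.** **Viewing and marking (8.3.2.2, general text).** The camera systems "will be used to identify tumor lesions under normal/visible light and fluorescent light prior to surgical excision of lesions", and again after excision. A lesion found under normal light or by palpation is marked O, and one found under fluorescence is marked x. "for those lesions that were also identified under normal light and/or by palpation", the x goes on top of the O to give ⊗. A lesion found only by fluorescence carries the x alone.

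**Times.** "The Investigator will record the start and stop time for each exposure to fluorescence", in a table of on and off times. There is no matching entry for when the O marks were made.

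**Partial nephrectomy (8.3.2.2).** The mass is viewed under visible and then fluorescent light, in that order of mention. Fluorescent lesions are entered on the schematic, and the paragraph ends: "Findings under visible light will also be recorded". The radical nephrectomy text names fluorescent before visible findings when it describes recording.

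**Appendix D, 19.4.7.** Before excision, images are captured by fluorescence and white light. Then: "The images will be evaluated to determine the extent of tumor involvement and confirm these assessments with normal visual examinations".

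**Appendix A, blinded-surgeon forms (19.1.1 and 19.1.2).** At each of four photograph stages, item a asks the reader to mark fluorescing regions with X. Item b asks the same reader to mark tumor areas on the white-light images with O.

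**Analysis.** In 12.8, "Kappa statistics will be used to assess agreement between visual and fluorescent images", and the number of lesions found by "usual visible/tactile conditions and/or palpation vs fluorescent imaging will be analyzed using a paired t-test". In 12.7, gross observation and fluorescence are each compared with pathology and immunohistochemistry.

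**The concern.** Both analyses in 12.8 treat the O reading as what the surgeon would have found without the agent. Section 8.3.2.2 provides no separate observer for the O marks, so on its plain reading one unblinded surgeon makes both. If fluorescence is seen first, it can draw the eye to a lesion that is then also judged visible and marked O. On the schematic, an x-only lesion becomes ⊗.

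The likely shift is in one direction. Agreement rises and the visual count rises, so the added yield of fluorescence falls. In the descriptive accuracy figures of 12.7, gross observation gains cancers that it did not find unaided. Added detection over visual observation is among the benefits argued in 5.1.2, so the shift would understate the agent on a quantity the protocol itself values. The order of marking cannot be recovered after surgery.

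**Working it through.** **1. Is an order required?** Setting the places side by side:

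| Place | What it indicates | Requires an order? |
|---|---|---|
| 8.3.2.2, general text | Visible light named first | No |
| 8.3.2.2, notation | x placed over O, implying O exists already | No; ⊗ looks the same whichever mark came first |
| 8.3.2.2, partial nephrectomy | Viewing: visible first. Recording: visible mentioned last | No |
| 8.3.2.2, radical nephrectomy | Viewing: visible first. Recording: fluorescent mentioned first | No |
| 19.4.7 | Images evaluated, then confirmed by visual examination | Suggests fluorescence can come first |
| Appendix A blinded forms | X item before O item, same reader | Order of the form |

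The text is unspecified and inconsistent. It is not uniformly in either direction.

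**2. Could the data show the order afterwards?** No. Fluorescence on and off times are captured, but white-light marking times are not. The equipment does not enforce a separation either: 19.4.2 describes simultaneous video and fluorescence images.

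**3. Is there a figure in the plan to reproduce?** Not for this comparison: no expected kappa, lesion count or power is given. The one probability in 12.3 concerns toxicity (1 − 0.9^20 = 0.878, stated as 88%) and does not bear on the point.

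**4. Direction and sensitivity, with assumed counts.** Assume 24 sites: 10 both, 6 x-only, 2 O-only and 6 neither. The schematic has no symbol for neither, so that cell is also an assumption. Let m of the 6 x-only lesions be back-marked O. Then:

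- O total = 12 + m; x total = 16; sites in agreement = 16 + m
- p_o = (16 + m)/24
- p_e = [(12 + m)·16 + (12 − m)·8]/576
- kappa = (p_o − p_e)/(1 − p_e)

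To follow the accuracy figures as well, assume that all 18 marked lesions are cancer.

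| m | kappa | Count, x minus O | Gross-observation sensitivity | Fluorescence sensitivity |
|---|---|---|---|---|
| 0 | 96/288 = 0.33 | +4 | 12/18 = 0.67 | 16/18 = 0.89 |
| 1 | 112/280 = 0.40 | +3 | 13/18 = 0.72 | 16/18 = 0.89 |
| 3 | 144/264 = 0.55 | +1 | 15/18 = 0.83 | 16/18 = 0.89 |
| 6 | 192/240 = 0.80 | −2 | 18/18 = 1.00 | 16/18 = 0.89 |

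The last column does not move, because turning x into ⊗ leaves the lesion fluorescence-positive.

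**5. A second set of assumed inputs.** Borrow the 34 fluorescent and 7 visual lesions that 5.1.2 cites from an ovarian study of a different agent. Assume that all 7 are among the 34, and add 34 double-negative sites. Let a share c of the 27 fluorescence-only lesions be back-marked. The visual count is 7 + 27c and the difference is 27(1 − c). With 68 sites and 34 of them fluorescent, p_e = 0.5, so kappa = 2(41 + 27c)/68 − 1.

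| c | Visual count | Difference | kappa |
|---|---|---|---|
| 0 | 7 | 27 | 0.21 |
| 0.10 | 9.7 | 24.3 | 0.29 |
| 0.25 | 13.75 | 20.25 | 0.40 |
| 0.50 | 20.5 | 13.5 | 0.60 |

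With 10 double-negative sites instead of 34, kappa runs 0.11, 0.15, 0.24 and 0.41. The direction is the same. The documents give no value for m or c, and both are zero if white light is in fact recorded first.

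**The case against.** The best defence is the notation rule. An x placed over an O presupposes that the O is there, and a fluorescence-only lesion is to carry an x alone, so back-marking would go against the scheme. The general text and the viewing sentences for both arms name visible light first. Section 19.4.7 is a device appendix for one camera and does not mention the schematic, and the images it has evaluated include white-light images. In Arm 1 the target is a mass already seen on CT, which leaves less room for fluorescence-only lesions. In Arm 2, the persistent lesions marked P after initial excision also show fluorescence yield and are not created by back-marking.

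Much of this stands. A reader might infer from the partial nephrectomy sentence that fluorescence is prescribed first. It gives order of mention only. A reader might also infer that the comparison is already contaminated, or that the count difference would reverse. The documents permit the unwanted order but do not mandate it for the schematic, and the reversal in the working needs every x-only lesion to be back-marked and two assumed O-only lesions.

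What does not stand is the notation rule as a safeguard. It defines a symbol. It neither forbids adding an O after fluorescence has been seen nor leaves a trace if that happens. The P lesions capture only what remains after the first excision.

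**Conclusion.** The point holds in limited form. White-light-first marking is implied in 8.3.2.2 but not required there or elsewhere, is not verifiable from the data captured, and sits poorly with 19.4.7 and the Appendix A forms. The visual-versus-fluorescence kappa, the paired lesion-count comparison and the gross-observation accuracy figures can be biased as a result. The blinded-reader forms matter too, because 12.8 does not say whether its image agreement uses the surgeon's schematic or the readers' marked photographs.

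The exposure is confined to secondary and descriptive results in a 20-patient pilot. A reader might extend it to the primary analysis, but fluorescence sensitivity and specificity in 12.7 and the 70% criterion in 12.3 depend on fluorescence status, which back-marking does not change. The size of any bias is unknown, and the tables show direction and sensitivity under assumed counts only. The conclusion rests on the same surgeon making both marks, which is the plain reading of 8.3.2.2. The change is worth making because it is cheap and the lost information cannot be recovered later.

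**What to change.** - **8.3.2.2 (both arms) and 19.4.7.** State that at each imaging stage (inside the trocar, after exposure of the tumor or nodal areas, during resection, after excision) the O marks for the field in view are completed and time-stamped before fluorescent light is turned on for that stage. They are not changed afterwards for that field. Newly exposed areas get their own white-light marks first.
- **Why by stage.** A single lock before the first use of fluorescence would not work. Appendix A takes fluorescent photographs inside the trocar, before the tumor or nodes are exposed, so lesions legitimately seen or felt later could not be marked.
- **Verification.** Compare the new time stamp with the recorded Time On. The existing table has rows for before excision, after initial excision and other, so it needs a row per stage.
- **Appendix A (19.1.1 and 19.1.2).** Put the white-light item first, and have blinded readers finish it before they see the fluorescent images.
- **Reconcile** the general, partial and radical nephrectomy texts of 8.3.2.2, the Appendix A forms and 19.4.7, so that they describe one sequence.

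The cost is one extra time stamp per stage, a brief pause before each fluorescence exposure and a reordered form. The change concerns recording only and leaves decisions on excision as they are. One limit remains: the fluorescence reading will still be made with the white-light findings known. That fits its stated role as an adjunct (19.4.1), but the kappa should not be described as agreement between two independent readings.
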